## **Research Plan**

Figure 1: Proposed screening procedures.

**Design:** Subjects will be screened for eligibility on Day 1 (**Figure 1**); those who meet the criteria will continue with the study.

The study design (**Figure 2**) will consist of up to three separate testing sessions, separated by approximately two weeks (+/- 3 days). One session will be a single, ~45-minute AIH protocol. The other will be 45 minutes of Sham AIH (ie. normoxia). Session order will be random. A third, optional session will be offered to eligible subjects (caffeine + AIH). Each session is expected to last ~3 hours, including equipment setup, patient positioning and pressure relief, rest breaks, AIH/Sham AIH, and post-intervention tests.

Subjects who elect to participate in Aim 3 will be scheduled for a third study session consisting of administration of 3 mg/kg of caffeine, followed by AIH 1 hour after caffeine consumption.

Study outcomes in Aim 1 include strength tests (respiratory and handgrip; MIP and MHGF), respiratory drive (P0.1), tidal breathing, and the hypoxic ventilatory response (HVR). In Aim 2, respiratory muscle recruitment will be tested at normoxic rest, during hypoxia, and with maximal voluntary inspiratory pressure generation. Aim 3 outcomes include maximal respiratory pressures, MHGF, tidal breathing, and saliva tests of caffeine metabolism.

Fig 2 Proposed study design.

**Subjects:** We propose to study 18 ALS patients and up to 30 healthy age/sex matched control subjects. Patients who meet study criteria will be identified by [name] (Co-I) through the UF adult neuromuscular clinic. The study PI will screen and consent patients. The PI will review the eligibility criteria. study procedures, participation risks, and the ability of subjects to withdraw from the study at any time.

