## Eligibility Criteria.

Subjects will be eligible to participate if they have a clinical diagnosis of ALS or are a healthy adult; are between 21 and 75 years of age; and have a baseline FVC >60% predicted for age, sex and height. Baseline FVC is routinely performed at every clinic for ALS patients. The AIH study team (PI or coordinator) will email a PFT report request to the clinic respiratory therapist, in advance of clinic. On the day of clinic, the respiratory therapist will upload the requested PFT reports directly into EPIC. After clinic, the AIH study coordinator will locate the PFT report in EPIC and save it to the electronic study binder. If the PFT report indicates the FVC is within study criteria, the subject can be contacted for an appointment. If the FVC falls below study eligibility, the patient will not be scheduled for a screening visit.

Patients will be classified into two groups: 1) uses no form of external respiratory support (IND); and 2) and uses non-invasive external respiratory support while sleeping for at least 2 nights per week to assist night time breathing or treat sleep apnea (NIV). Since 4-6 subjects in each group may fail to meet all eligibility criteria or attend the second testing session, we request to enroll up to 18 patients with ALS, with the goal of completing all study procedures in 12 patients. In addition, we request enrollment of up to 30 healthy controls to complete all study procedures in 20 (up to 20 healthy controls may be needed as a reference set for the EMG data analysis described on *page 10*). The healthy controls will be recruited via listings for this study on CT.gov and the StudyConnect website.

Patient and control participants are ineligible if they: are pregnant, have diagnosed cardiovascular disease, have a BMI >35 kg/m^2, currently take selective serotonin reuptake inhibitors (SSRI), have a history of seizures, have a history of hospitalization for sepsis, had a respiratory infection or took antibiotic medications within the past 4 weeks, use external respiratory support during any waking hours, participate in a pharmaceutical trial to treat ALS, or have any other medical condition the PI ([name]) or medical director ([name]) identify would make it unsuitable to participate.

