## Aim 1 Dependent Variables – Maximal Voluntary Contractions

- Maximal respiratory pressures maximal voluntary static contractions of the inspiratory or expiratory muscles against a closed valve, measured at the mouth (64). Sniff nasal inspiratory pressure measures inspiratory force generation at the nose. This more natural maneuver has lower variability and learning effects (65) and appears to decline in conjunction with the need for nocturnal ventilation in ALS (66, 67). The test will be repeated until 3 measurements are obtained within 10% variability; a minimum 20-second rest will be provided between measurements. Maximal inspiratory pressures will be measured at baseline and 60 min post-AIH.
- Peak cough flow the maximal expiratory airflow measured through a facemask during a maximal-effort voluntary cough. Subjects will repeat 3-5 voluntary coughs to achieve 3 measurements within 10% variability. The peak cough flow will be measured at baseline and 30 min post- intervention.
- Maximal voluntary grip force maximal static voluntary handgrip contractions will be evaluated in a seated position with the arm at the side and elbow flexed to 90 degrees. The test will be repeated until 3 measurements are obtained with <10% variability, and a minimum 15-second rest between measurements. Significant gains in isometric force have been reported with a single AIH session in patients with spinal cord injury. Grip strength will be measured at baseline, 30 and 60 minutes post-intervention.

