### **Statistical Analysis**

The outcomes for both aims are largely quantitative and continuous. Sample distributions and summary statistics will be calculated for each outcome, and non-linear data distributions will be transformed as needed. Study outcomes for Aims 1-2 include acute changes in voluntary strength, resting ventilation, and respiratory drive. Each of these will be evaluated with 3-way repeated measures ANOVAs. Factors will be subject group (patient vs control), AIH condition (AIH vs Sham AIH), and time (pre, 0 minutes post, 30 minutes post, 60 minutes post); Tukey's post hoc test will be used to assess individual differences. A separate ANOVA will compare the independent effect of caffeine on motor function 60 minutes post-AIH. We will work with BERD to use genetic testing results to model independent effects of caffeine metabolism genotype on AIH motor facilitation, as pilot data to estimate sample size for a larger, future project. For the analysis of sEMG Response Vector and Similarity Index, baseline FVC will be used as a covariate. These will be tested with 2-way repeated measures ANOVAs (AIH only, factors: subject group

and time). Relationships between variables will be evaluated with Pearson's correlation. Statistical significance will be p<0.05.

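### The Aims 1-2 ANOVA uses the session baseline as a level of time, so the condition-by-time contrast is a difference of change scores: valid, but less precise than a baseline-adjusted contrast unless visit-to-visit variation dominates

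*Combined protocol and SAP*

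**What the plan says.** Statistical Analysis introduces the outcomes this way: "Study outcomes for Aims 1-2 include acute changes in voluntary strength, resting ventilation, and respiratory drive". It then states: "Each of these will be evaluated with 3-way repeated measures ANOVAs". The factors are subject group, "AIH condition (AIH vs Sham AIH), and time (pre, 0 minutes post, 30 minutes post, 60 minutes post". On follow-up comparisons it says only: "Tukey's post hoc test will be used to assess individual differences". No model term or contrast is named as the test of AIH.

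One covariate appears, and only for the EMG outcomes: "For the analysis of sEMG Response Vector and Similarity Index, baseline FVC will be used as a covariate". The outcome's own session baseline is not a covariate for strength, ventilation or drive.

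On design, Research Plan says: "Session order will be random". The sessions are about two weeks apart. For MIP, the Aim 1 section says: "Maximal inspiratory pressures will be measured at baseline and 60 min post-AIH". Grip and P0.1 have two post times (30 and 60 minutes). Tidal breathing has three (immediately after, 30 and 60 minutes). Eligibility Criteria gives the patient number: up to 18 enrolled, "with the goal of completing all study procedures in 12 patients". The target for healthy controls is 20 completers.

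**The concern.** The natural reading of acute changes, with the baseline as a time level, is that the condition-by-time term carries the AIH effect. That term subtracts each session's baseline in full. Full subtraction is optimal only when all within-subject variation lies between visits. If subjects are stable from one visit to the next, the baseline difference between sessions is pure measurement noise, and subtracting it adds noise to the answer.

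Both sessions of every subject have a baseline, and order is random. Without carryover after two weeks, expected baselines are equal under AIH and sham. (Background reports effects of a single session lasting up to four hours.) A baseline covariate with an estimated coefficient therefore targets the same effect. At stake is precision on MIP, grip and the resting measures with 12 patient completers, in a study sized by time and budget whose purpose is strong pilot data.

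**Working it through.** **Inputs.** From the documents: 12 patient and 20 control completers; the post times above; significance at 0.05 (two-sided assumed). There is no stated power, SD or correlation to reproduce. Assumption: b = visit-to-visit variance / (visit-to-visit + within-session variance), not given, shown from 0 to 0.9.

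**Step 1: what the term is.** MIP has one baseline and one post reading per session. On simulated 2 x 2 data, the condition-by-time F was 0.9255 and the squared t for the difference of change scores was 0.9255, so they are the same test.

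**Step 2: variances, one post time.** Let D_pre and D_post be the AIH-minus-sham differences, each with variance t², correlation b.
- Change score: Var(D_post - D_pre) = 2t²(1-b).
- Baseline-adjusted: t²(1-b²).
- Ratio: 2(1-b)/(1-b²) = 2/(1+b).

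**Step 3: several post times.** For the mean of k post times with equal correlations the ratio is (k+1)/(1+kb). At b = 0 it is 2, 3 and 4 for k = 1, 2, 3. At b = 0.5 it is 1.33, 1.50 and 1.60. At b = 0.9 it is 1.05, 1.07 and 1.08.

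**Step 4: cost of estimating the slope.** With 12 patients alone the adjusted variance rises by 1 + 1/(12-3) = 1.11. The realised ratio is then 2.0/1.11 = 1.80 at b = 0, 1.20 at 0.5, 1.00 at 0.8 and 0.95 at 0.9. With one slope over 32 completers and two intercepts the factor is 1 + 1/(32-4) = 1.036, giving 1.93 at b = 0 and 1.02 at b = 0.9.

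**Step 5: simulated power**, one post time, no true period shift. The effect is set so that the patients-only change score has 80% power; the two-group change score with pooled error then has about 84%.

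| b | 2/(1+b) | Patients-only slope | Common slope | Common slope + period |
|---|---|---|---|---|
| 0 | 2.00 | 96% | 98% | 98% |
| 0.25 | 1.60 | 91% | 96% | 95% |
| 0.5 | 1.33 | 86% | 92% | about 90% |
| 0.75 | 1.14 | 80% | 88% | 86% |
| 0.9 | 1.05 | 77% | 85% | 84% |

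The common-slope columns assume equal slope and error variance in both groups. Type I error was about 5% throughout. If slope and period are both fitted in the 12 patients alone, the gain is about nil at b = 0.5, and about 5 to 7 points are lost at b = 0.75 to 0.9.

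**Step 6: why period is needed.** A shift between sessions cancels from the change score but only partly from a regression without a period term. The protocol states no balancing of order. Under simple randomisation, a split of 8:4 or worse among 12 has probability 2 x 794/4096 = 39%. With b = 0, no AIH effect and a period shift of one SD of a single reading, the intercept without a period term is biased by 0.22 SD at 8:4 and 0.35 SD at 9:3. Type I error at 9:3 is about 8.4%. Adding the period term removes the bias and restores 5%.

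**The case against.** Five points can be made for the plan.

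- **No term is named.** A reader might infer that every AIH-versus-sham effect from this ANOVA is a difference of change scores. The documents do not support that. It holds for the condition-by-time contrast. A Tukey comparison of the two post cells uses two readings, not four, and ignores baseline. The condition main effect averages in the untreated baseline, so it carries only 1/2, 2/3 or 3/4 of a constant effect for 1, 2 or 3 post times. Neither alternative uses the baseline well.
- **b is probably not 0.** The disease progresses, sessions are two weeks apart and travel fatigue may affect performance. Repeating strength tests until three readings agree within 10%, and taking five P0.1 readings, reduces within-session noise. All of this raises b and shrinks the gain. This stands, though nothing shows that b is close to 1.
- **The larger power gains borrow from controls.** They assume that ALS patients and healthy adults share a slope and an error variance. The documents offer no support for this, so it is a real cost.
- **Results have been seen.** Background reports early findings in six subjects, so the model would change after some outcomes were known. This stands, and is a reason to date the change and keep the planned contrast in view.
- **It is a valid pilot analysis with no power claim.** True. The point is efficiency only.

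**Conclusion.** The condition-by-time contrast, the reading that best fits acute changes, is a valid and unbiased estimate that uses the session baseline inefficiently. For one post time its variance is 2/(1+b) times the adjusted variance: 2.0, 1.33 and 1.05 at b = 0, 0.5 and 0.9, before slope estimation.

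A reader might infer that the plan doubles the variance, or that its AIH test is biased. Neither follows. Doubling is the b = 0 extreme for a single post time, and the test keeps its level. With a common slope and a period term, the gain over about 84% power runs from some 14 points at b = 0 to nil or a loss of 1 to 2 points at b near 0.9.

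These figures rest on equal variances at pre and post, equal correlations across times, no carryover at two weeks and, for the pooled fit, a shared slope and error variance. The change is worth making because the baselines are already collected, but the size of the benefit is unknown.

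**What to change.** In Statistical Analysis, for the Aims 1-2 strength, ventilation and drive outcomes:

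1. Remove the baseline from the levels of time.
2. For each outcome, regress (AIH post - sham post) on (AIH pre - sham pre), with a separate intercept per group, one common slope across all completers, and a period (session order) term coded +1/2 and -1/2. The patient intercept, at zero baseline difference, is the AIH effect in patients.
3. Name the post measure in advance: 60 minutes for MIP; one stated post time, or the mean of the post times, for grip, P0.1 and tidal breathing.
4. Keep the change-score contrast as a sensitivity analysis, and record that the change was made after early results in six subjects.

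No new data, visits or procedures are needed. The cost is one or two degrees of freedom, the assumption that patients and controls share a slope and error variance, and about 1 to 2 points of power if b is near 0.9. Fitting slope and period in the 12 patients alone would avoid the shared-slope assumption but cost about 5 to 7 points at b = 0.75 to 0.9.

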Early results (n=6) indicate respiratory motor gains in some, but not all subjects following AIH. While the primary means of AIH motor facilitation occurs via serotonergic signaling, AIH motor facilitation can occur through an alternative, adenosine-mediated signaling pathway (38, 39). The serotonergic and adenosine pathways compete for dominance via cross-inhibition, and when activated equally, they cancel one another (19, 40). However, recent basic science data from our group indicates that pre-treatment with an adenosine receptor antagonist can restore AIH-induced respiratory motor function (41). Aim 3 is an optional/exploratory aim evaluating whether co-administration of lowdose (3 mg/kg) caffeine, a non-selective adenosine receptor antagonist, augments respiratory and grip function to a greater degree than AIH alone. Caffeine is rapidly absorbed, and then degraded to paraxanthine in the liver via Cytochrome P450 1A2 (CYP1A2). Maximal serum concentrations are reached within ~1 hour of consumption.(42) The plasma half-life of caffeine is ~4 hours, but ranges from 2-8 hours between individuals.(43) Caffeine freely crosses the blood-brain barrier and enters the CNS; 3 mg/kg of caffeine inhibits A2A (~60%) and A1 receptors (50%); 6 mg/kg of caffeine yields ~75% A2A and ~65% A1 receptor inhibition.(44) Caffeine also inhibits phosphodiesterase activity, but only at doses >9 mg/kg.(45) Caffeine is the most widely

used psychoactive drug worldwide (46), and is considered safe for use in most neurodegenerative disorders, including ALS (47, 48).

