## Specific Aims

**Aim 1: Test the hypothesis that a single AIH trial increases maximal respiratory and non-respiratory motor function in ALS.** Dependent variables will include: maximal inspiratory pressure (MIP) and maximal handgrip force (MHGF). We will address the following questions:

- a. Does AIH increase voluntary inspiratory pressure generation?
- b. Does AIH increase maximal handgrip force?
- c. Are baseline MIP and MHGF inversely related to AIH-induced facilitation?

Aim 2: Test the hypothesis that a single AIH trial increases resting respiratory motor function in ALS. Dependent variables will include: resting tidal volume, respiratory EMG at rest, resting ventilatory drive. Three questions will be addressed:

- a. Does AIH increase resting tidal volume?
- b. Does AIH increase the resting ventilatory drive?
- c. Does AIH increase respiratory muscle activation and restore more normal respiratory muscle recruitment patterns?

Aim 3: Test the hypothesis that pre-treatment with caffeine will augment respiratory and non-respiratory motor function. Dependent variables will include: maximal respiratory pressures, maximal grip force, resting tidal volume, EMG. Three questions will be addressed:

- a. Does acute consumption of caffeine enhance AIH-induced facilitation of respiratory and non-respiratory motor function?
- b. Is there a difference in AIH-induced facilitation of respiratory and nonrespiratory motor function between slow and fast caffeine metabolizers?
- c. Does acute consumption of caffeine improve the AIH-induced increase in respiratory muscle activation?

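### Aims 3a and 3c ask whether caffeine enhances AIH-induced facilitation, but with no caffeine + sham session the planned data give only caffeine's own effect plus any interaction, probably mixed with session order

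*Combined protocol and SAP*

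**What the plan says.** - Specific Aims gives the Aim 3 hypothesis as "Test the hypothesis that pre-treatment with caffeine will augment respiratory and non-respiratory motor function". Question 3a is "Does acute consumption of caffeine enhance AIH-induced facilitation of respiratory and non-respiratory motor function"; 3b is "Is there a difference in AIH-induced facilitation of respiratory and nonrespiratory motor function between slow and fast caffeine metabolizers"; 3c puts the 3a question for respiratory muscle activation.
- The Background words Aim 3 more narrowly: whether caffeine with AIH "augments respiratory and grip function to a greater degree than AIH alone". The section headed Our plan likewise speaks of caffeine's effect on motor performance after AIH.
- Research Plan describes one AIH and one sham session, then states "Session order will be random", and only then introduces an optional third session of caffeine + AIH. Eligibility Criteria also calls that visit the third. No caffeine + sham session is described anywhere.
- In the caffeine session, baseline tests come first, then caffeine, and AIH starts one hour later (Independent Variable section, caffeine item).
- Maximal inspiratory pressure (MIP) is tested at baseline and 60 minutes, and grip at baseline, 30 and 60 minutes. Aim 3 takes both over from Aim 1. EMG and breathing are monitored continuously.
- Statistical Analysis: "A separate ANOVA will compare the independent effect of caffeine on motor function 60 minutes post-AIH". That sentence names no comparator and no handling of baseline.
- Possible Discomforts and Risks says that caffeine at 3-6 mg/kg can itself increase limb strength and possibly respiratory muscle strength.

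**The concern.** Facilitation by AIH means AIH relative to sham. To say that caffeine enhances it is to claim that the AIH-minus-sham difference is larger with caffeine than without. The with-caffeine half of that comparison needs a caffeine + sham measurement, or at least a test after caffeine and before AIH. Neither is planned for MIP or grip. Nor is caffeine's independent effect, the term used in Statistical Analysis, available: that would be caffeine versus no caffeine without AIH.

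A positive result could therefore be reported as a yes to 3a when caffeine has merely raised performance on effort-dependent strength tests. Because the study is meant to supply pilot data for a grant application, that reading could carry into the design of the next study.

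**Working it through.** The documents give no number of participants, SD or effect size for Aim 3, so there is no planned figure to reproduce. Results below are structural or in SD units.

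**1. What the sessions identify.** Let m be the sham mean, A the AIH effect, C the caffeine effect without AIH, and I the interaction.

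| Session | Expected value | Planned? |
|---|---|---|
| Sham | m | yes |
| AIH | m + A | yes |
| Caffeine + AIH | m + A + C + I | yes, optional |
| Caffeine + sham | m + C | no |

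Question 3a concerns I = (caffeine + AIH − caffeine + sham) − (AIH − sham). The planned contrast, caffeine + AIH − AIH, equals C + I. The three planned rows have rank 3 for 4 parameters: A and C + I are estimable, C and I separately are not. The fourth row would raise the rank to 4. As an illustration, (C, I) = (0.5, 0), (0, 0.5) and (0.8, −0.3) all give C + I = 0.5. No enhancement, pure enhancement and antagonism look identical at any sample size.

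**2. No substitute within the session.** Baseline precedes caffeine, so change from baseline contains C. For resting EMG a value after caffeine and before AIH might be extracted, but Statistical Analysis plans no such analysis, so 3c is in the same position as 3a.

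**3. Can C be taken as zero at the 60-minute test?** The protocol's own risk section says not. On its kinetics ("Maximal serum concentrations are reached within ~1 hour of consumption"; "The plasma half-life of caffeine is ~4 hours, but ranges from 2-8 hours between individuals"), the test falls 60 + 45 + 60 = 165 min, or 2.75 h, after dosing, which is 1.75 h after a 1-hour peak. Assuming first-order decay, the fraction of peak remaining is 2^(−1.75/h): 0.55, 0.74 and 0.86 for half-lives h of 2, 4 and 8 h.

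**4. What a caffeine-only effect would do.** Take I = 0, a two-sided 0.05 paired t-test (sidedness is not stated), and C = d within-subject SDs per session. The non-centrality is d√(n/2) on n − 1 df. The probability of a significant result is:

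| n | d = 0.5 | d = 1.0 |
|---|---|---|
| 6 | 0.11 | 0.29 |
| 12 | 0.20 | 0.61 |
| 20 | 0.32 | 0.85 |
| 32 | 0.49 | 0.97 |

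Under 3a's wording each such result would be a false claim of enhancement. The values of d are assumptions.

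**5. Precision of the contrast that can be estimated.** The 95% CI half-width in SDs of the paired difference is t(0.975, n − 1)/√n. The goal is 12 ALS completers and 20 controls (Eligibility Criteria); n = 6 assumes half the patients accept, and n = 32 is 12 + 20.

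- n = 6: 2.571/2.449 = 1.05
- n = 12: 2.201/3.464 = 0.64
- n = 20: 2.093/4.472 = 0.47
- n = 32: 2.040/5.657 = 0.36

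**6. Session order.** If caffeine is always third and session effects are unrestricted, only (third-session effect + C + I) is estimable. If a linear trend shared by all participants is assumed, it can be adjusted for, at a cost. Take n caffeine participants among N who complete both other sessions, with AIH/sham order balanced. In change-score SD units the variance of C + I is 1.5/n + 0.5/N unadjusted and 1.5/n + 5/N adjusted.

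- n = N = 12: √0.1667 = 0.41 and √0.5417 = 0.74, ratio 1.80
- n = 6, N = 12: √0.2917 = 0.54 and √0.6667 = 0.82, ratio 1.51
- n = 12, N = 32: √0.1406 = 0.375 and √0.2813 = 0.53, ratio 1.41

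**The case against.** The best defence is that the protocol already asks the narrower question. The Background compares with AIH alone, Our plan speaks of performance after AIH, and the analysis sentence is tied to the time after AIH and never mentions enhanced facilitation. The Aim 3 hypothesis ("Test the hypothesis that pre-treatment with caffeine will augment respiratory and non-respiratory motor function") can also be answered by that comparison. All of this stands, and it limits the point to wording. It does not correct 3a and 3c, which still ask about facilitation, or the description of the contrast as an independent effect.

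It is also fair that Aim 3 is optional and exploratory, and that nothing in the documents says an interaction will be claimed. The misreading is a risk, not a stated intention.

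A reader might infer that the restated contrast is a clean caffeine effect. The text does not support that. Two sections call the caffeine visit the third, and the sentence on random order comes before that visit is introduced, so it probably always comes last. Equally, the documents do not prove it: third could mean additional, and Figure 2, which is not shown in the available text, may settle it.

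A reader might also infer that 3b cannot be answered. It has two readings. Genotype can be related to AIH-versus-sham facilitation in the caffeine-free sessions without this problem; the limit applies only if the caffeine session is used.

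**Conclusion.** The point holds in limited form. The planned sessions identify C + I, and neither 3a's enhancement nor caffeine's independent effect. This is a matter of design rank and rests on no assumed SD or sample size. Aim 3c is limited in the same way unless a resting EMG value after caffeine and before AIH is analysed. If caffeine is always last, the contrast also carries any session effect that change from baseline does not remove.

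The probabilities, interval widths and trend-adjusted standard errors depend on assumed effects, assumed uptake of Aim 3 and, for the last, a linear shared trend. They show scale only.

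It would go too far to conclude that Aim 3 is unanswerable or that the trial needs a fourth session: the Aim 3 hypothesis and the Background question can be addressed with the planned data, subject to the session-order caveat. Aims 1 and 2 are not affected. This is a modest correction that should be made before Aim 3 is analysed.

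**What to change.** 1. In Specific Aims (3a and 3c) and in the Aim 3 sentence of Statistical Analysis, state the target as the added effect of caffeine given with AIH compared with AIH alone. Analyse it as the within-subject difference between the two sessions in change from each session's own baseline to 60 minutes, with a 95% CI. Do not report it as caffeine enhancing AIH-induced facilitation or as caffeine's independent effect.
2. State where the caffeine session falls in the order. If it is always last, say that the contrast includes any session effect left after subtracting baseline, and that it cannot be estimated if session effects are unrestricted.
3. For 3b, say which sessions are used. If the caffeine session is among them, apply the same limit on interpretation.

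The cost is a few sentences and one analysis definition, using data already planned. No extra session is requested. A caffeine + sham session would identify the interaction, but it means another visit of about 3 hours, and the interaction's standard error would be √(4/n)/√(2/n) = 1.41 times that of the restated contrast. It is better considered for the larger future project.
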